8.2.2. Analysis of the Proportion of PGI-C Responders

The PGI-C secondary endpoint will be tested for the following hypothesis:

H₃₀: The proportion of PGI-C responders at Visit 6 does not differ between PH94B and placebo.

H₃₁: The proportion of PGI-C responders at Visit 6 does differ between PH94B and placebo.

The estimand for the PGI-C secondary efficacy endpoint includes the same population, treatment, and anticipated intercurrent events as the primary estimand. The variable of interest is the proportion of PGI-C responders at Visit 6. The proportion of PGI-C responders will be calculated as described in Section 6.1.7.4. The population-level summary measure is the difference in the proportion of PGI-C responders between PH94B-treated and placebo-treated subjects at Visit 6.

The analysis for this endpoint will be exactly parallel to the one described for the CGI-I secondary endpoint in Section 8.2.1.

8.2.3. Secondary Efficacy Analysis of Change from Baseline in ADNM Total Score

The ADNM secondary endpoint will be tested for the following hypothesis:

H₁₀: Mean change in ADNM total score from Visit 2 (Baseline) to Visit 6 does not differ between PH94B and placebo.

H₁₁: Mean change in ADNM total score from Visit 2 (Baseline) to Visit 6 does differ between PH94B and placebo.

The estimand for the ADNM secondary efficacy endpoint is the same as that for the primary endpoint, except that it uses the ADNM total scores as the variable of interest. Change from baseline to Visit 6 in ADNM total score will be analyzed analogously to the primary endpoint. Multiple imputation will not be performed.

Descriptive summaries will be provided for observed ADNM total scores and changes from baseline by visit and by treatment group.

8.2.4. Secondary Efficacy Analysis of Change from Baseline in IADQ Total Score

The IADQ secondary endpoint will be tested for the following hypothesis:

H₁₀: Mean change in IADQ total score from Visit 2 (Baseline) to Visit 6 does not differ

between PH94B and placebo.

H₁₁: Mean change in IADQ total score from Visit 2 (Baseline) to Visit 6 does differ between PH94B and placebo.

The estimand for the IADQ secondary efficacy endpoint is the same as that for the primary endpoint, except that it uses the IADQ total scores as the variable of interest. Change from baseline to Visit 6 in IADQ total score will be analyzed analogously to the primary endpoint. Multiple imputation will not be performed.

Descriptive summaries will be provided for observed IADQ total scores and changes from baseline by visit and by treatment group.

8.3. Exploratory Efficacy Analysis

To evaluate the efficacy of PH94B over time, observed values and changes from baseline in HAM-A total scores will be summarized by visit and by treatment group. Summaries of CGI-I and PGI-C scores by visit and by treatment group will be displayed with the secondary efficacy analyses.

The differences in changes from baseline between the PH94B and placebo groups in HAM-A total scores at Visits 3, 4, and 5 will be assessed using the ANCOVA analysis described in Section 8.1 for the observed data.

The ADNM and IADQ observed subscores and changes from baseline will be displayed in by-subject listings.

9. Safety and Tolerability Analysis

Safety in this study will be evaluated based on data collected on AEs, clinical laboratory assessments, vital signs, 12-lead ECGs, and physical examinations including examination of the nasal passages, C-SSRS, MADRS scores, and PWC-20 scores.

All safety analysis reporting will be based on the Safety population (as defined in Section 5).

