	
investigational product (IP) and will be dispensed a 1-week supply of PH94B or placebo. Subjects will then commence 4 weeks of double-blind treatment with the randomized IP 4 times per day.
 
Subjects will return for weekly site visits (Visits 3, 4, and 5), in which the subject will return the IP vials dispensed at the previous visit and receive new vials. Concomitant medications and adverse events (AEs) will be recorded. During these visits, the HAM-A, Patient Global Impression of Change (PGI-C), Clinical Global Impression - Improvement (CGI-I), CGI-S, and C-SSRS will be completed. Vital signs will be collected, and nasal passages will be examined.
 
When the subject returns for Visit 6, besides the assessments completed at Visits 3 through 5, the subjects will complete the MADRS, ADN, and IADQ; and have a physical examination, ECG, laboratory tests (chemistry and blood), urinalysis, urine drug screen, and urine pregnancy test conducted. Any remaining IP vials will be collected. The subject will then come back after a 1-week washout period for the Follow-up visit (Visit 7). During this visit, AEs and concomitant medications since the last visit will be collected and the HAM-A, C-SSRS, and the 20-item Physician Withdrawal Checklist (PWC-20) will be completed.
 
For each visit following Baseline (Visit 2), a \pm 2-day window will be allowed.
 
Safety considerations:
 
Safety and tolerability of PH94B will be assessed and summarized through changes from screening in clinical laboratory values, ECGs, physical examinations, and vital sign assessments following exposure to PH94B, as well as by comparison of AEs reported during treatment with the IP. To date, limited exposure to PH94B (<2 weeks, <4 doses per day) in over 200 subjects has resulted in no serious AEs (SAEs) and no AEs occurring with statistically greater frequency for the PH94B group than for the placebo group. In addition, the PWC-20 will be administered to document any withdrawal effects that may be occurring.

PLANNED NUMBER OF SUBJECTS	Forty adult subjects will be randomized 1:1 to PH94B or placebo.

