	
Interview Guide for the HAM-A (SIGH-A), after 4 weeks of randomized treatment with the study medication
 
4. Population-level summary measure: Difference in mean HAM-A total score between PH94B-treated and placebo-treated subjects after 4 weeks of treatment5. Anticipated intercurrent event: Treatment discontinuation prior to the planned assessment time frame
SAMPLE SIZE DETERMINATION	A sample size of 40 subjects was selected based on information from published studies on treatments for adjustment disorder suggesting that a clinically meaningful effect size could be estimated using a sample size of 40.
STUDY AND TREATMENT DURATION	
The sequence and maximum duration of the study periods will be as follows:
 
1. Screening and washout: [REDACTED]2. Treatment period: From Visit 2 (Baseline) through Visit 6 (End of Treatment)3. Follow-up period: Follow-up visit (Visit 7) conducted approximately 1 week after last treatment 
The maximum study duration for each subject is approximately 10 weeks.
 
The maximum treatment duration for each subject is 4 weeks.

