2.1.3. Exploratory Objective

An exploratory objective of the study is to evaluate efficacy of PH94B over time during the 4-week treatment period.

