2.2.1.3. Exploratory Efficacy Endpoint(s)

The exploratory efficacy endpoints are mapped to the exploratory objective as follows:

Exploratory Objective	Exploratory Efficacy Endpoints
An exploratory objective of the study is to evaluate efficacy of PH94B over time during the 4-week treatment period.	Summaries and changes from baseline in HAM-A at Weeks 1, 2, and 3. Summaries and changes from baseline in ADNM subscales at Week 4. Summaries of CGI-I and PGI-C at Weeks 1, 2, 3, and 4 (each week).

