4.1. Introduction

Data processing, tabulation of descriptive statistics, calculation of inferential statistics, and graphical representations will primarily use Statistical Analysis System Software (SAS) (release 9.4 or higher). If the use of other software is warranted, the final SAP and the statistical methodology report will detail what software was used for what purposes.

Continuous (quantitative) variable summaries will include the number of subjects (n) with non-missing values, mean, SD, median, minimum, and maximum. The minimum and maximum will be reported with the same degree of precision (i.e., the same number of decimal places) as the observed data. Measures of location (mean and median) will be reported to 1 degree of precision more than the observed data and measures of spread (SD) will be reported to 2 degrees of precision more than the observed data.

Categorical (qualitative) variable summaries will include the frequency and percentage of subjects who are in the category or each possible value. The denominator for the percentage calculation will be based upon the total number of subjects in the study population for the treatment groups unless otherwise specified. Percentages will be presented to 1 decimal place. Counts of zero will be presented without percentages.

Unless otherwise indicated, all statistical tests will be conducted at the 0.05 significance level using 2-tailed tests, and p values will be reported. Corresponding 95% confidence intervals (CIs) will be presented for statistical tests. All p values will be displayed in four decimals and rounded using standard scientific notation (e.g., 0.XXXX). If a p value less than 0.0001 occurs it will be shown in tables as < 0.0001 ; similarly, if a p value greater than 0.9999 occurs, it will be shown in tables as > 0.9999 . Confidence intervals will be reported to 1 degree of precision more than the observed data.

This study is considered a Phase 2a exploratory study under an IND application for PH94B targeting AjDA. Statistical tests will be applied and interpreted to determine feasibility and best approaches for potential Phase 2b and Phase 3 studies.

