6.1.4. Handling of Dropouts or Missing Data

Data will be included in the analysis according to the analysis visit windows described in Section 6.1.5.

Treatment of intercurrent events (ICEs) will be as described in Table 3. Briefly, subjects who withdraw from the study after treatment begins will be encouraged to complete an Early Termination Visit where all Visit 6 assessments will be performed. If the subject is lost to follow-up or otherwise unable to complete the Visit 6 assessments or if the subject uses a prohibited medication prior to the planned end of treatment, the Visit 6 HAM-A score will be set to missing. If the fraction of missing change from baseline to Visit 6 HAM-A total scores in the ITT population is ≤ 0.05 , missing change scores will be imputed with treatment group mean change scores for the primary efficacy analysis. If the fraction of missing change scores is greater than 0.05, multiple imputation of the change from baseline to Visit 6 HAM-A total scores will be carried out for the primary efficacy analysis. The fraction of missing change from baseline to Visit 6 HAM-A total scores will be computed as described in Section 6.1.7.2. The multiple imputation procedure will not impute individual HAM-A item scores or HAM-A total scores; only change from baseline to Visit 6 HAM-A total scores will be imputed. Other efficacy and safety data will not be imputed and will be analyzed as observed.

Table 3: Strategies for Intercurrent Events

ICE	Strategy for Addressing ICE
Treatment discontinuation following randomization but prior to Week 4.	While on Treatment Strategy The research objectives seek to understand the response to PH94B compared to placebo while subjects are actively using the study medication. Subjects who discontinue will undergo an Early Termination Visit and provide all Visit 6 outcome measures and safety assessments for the efficacy analysis.

ICE	Strategy for Addressing ICE

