ITT Population

Study Visit [1] Statistic	PH94B (N=XX)		Placebo (N=XX)	
	Observed	CFB	Observed	CFB
Visit 6 (End of Treatment/Early Termination)				
n	XX	XX	XX	XX
Mean (SD)	XX.X (XX.XX)	XX.X (XX.XX)	XX.X (XX.XX)	XX.X (XX.XX)
Median	XX.X	XX.X	XX.X	XX.X
Min, Max	(XX, XX)	(XX, XX)	(XX, XX)	(XX, XX)
LS Mean (SE)		XX.X (X.XX)		XX.X (X.XX)
95% CI for LS Mean CFB		(XX.X, XX.X)		(XX.X, XX.X)
P value for Difference from Baseline		X.XXXX		X.XXXX
LS Mean Difference from Placebo (SE)		XX.X (X.XX)		XX.X (X.XX)
95% CI for Difference from Placebo		(XX.X, XX.X)		(XX.X, XX.X)
P value for Difference from Placebo		X.XXXX		X.XXXX

Abbreviations: ANCOVA = analysis of covariance; CFB = change from baseline; CI = confidence interval; HAM-A = Hamilton Anxiety Scale; LS = least-squares; SD = standard deviation; SE = standard error.

Note: Subjects are summarized by planned treatment. The HAM-A is a questionnaire used to assess anxiety and is completed by trained personnel. It consists of 14 items, each scored on a 5-point scale rating anxiety from "Not Present" to "Very severe". The HAM-A total score is the sum of the individual item scores. Baseline is defined as the HAM-A total score from Visit 2 (Baseline). Change from baseline is calculated as result – baseline result. Least squares mean, LS mean differences (treatment – placebo), 95% CIs, and P values were obtained from an ANCOVA model with change from baseline to Visit 6 in HAM-A total scores as the outcome, treatment group as a factor, and baseline HAM-A total score as a covariate.

[1] Visit 6 (End of Treatment/Early Termination) includes data from subjects who either completed Visit 6 (End of Treatment) or who discontinued from the study and completed an early termination visit.

Reference Listing: 16.2.6.1

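### Weekly HAM-A treatment differences use one data rule at Weeks 1-3 and another at Week 4, so unequal intercurrent events between arms can create a false late step

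*SAP*

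**What the plan says.** The exploratory objective (SAP 2.1.3) is to "evaluate efficacy of PH94B over time during the 4-week treatment period". The HAM-A endpoint attached to it (SAP 2.2.1.3) is narrower: "Summaries and changes from baseline in HAM-A at Weeks 1, 2, and 3".

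**Visits 3 to 5.** SAP 8.3 plans a separate ANCOVA at each visit: "HAM-A total scores at Visits 3, 4, and 5 will be assessed using the ANCOVA analysis described in Section 8.1 for the observed data". SAP 6.1.4 says that efficacy data other than the primary change score are not imputed. The results go in Table 14.2.6.1, which stops at Visit 5.

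**Visit 6.** The treatment difference appears in Table 14.2.1.1, whose footnote [1] says that Visit 6 "includes data from subjects who either completed Visit 6 (End of Treatment) or who discontinued from the study and completed an early termination visit". Under SAP 6.1.4 the Visit 6 score is set to missing if the subject used a prohibited medication before the planned end of treatment. Missing changes are then filled, and "only change from baseline to Visit 6 HAM-A total scores will be imputed". The deletion rule names Visit 6 only.

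**Both.** SAP 6.1.5 analyses efficacy data at the nominal visit, without windows. SAP 8.1 bases the by-visit descriptive summaries on observed values. Protocol 8.3 asks subjects who discontinue to keep attending the weekly visits and makes the Visit 6 assessments the fallback. SAP 3.2 and 6.1.4 describe only the early-termination visit.

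**The concern.** To see efficacy across the four weeks, a reader must join the Visit 3 to 5 differences in Table 14.2.6.1 to the Visit 6 difference in Table 14.2.1.1. The two sets of numbers treat the same subject differently.

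- A subject who stops in Week 2, gives one early-termination assessment and does not return is absent from the later weekly rows, then appears at Week 4 with a Week 2 score.
- A subject who takes a prohibited medication in Week 2 keeps the Visit 4 and Visit 5 scores but loses the Visit 6 score.

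An apparent late gain or fading of effect could therefore reflect data handling. SAP section 4 says the study's tests will inform the approach to Phase 2b and Phase 3, and a time-course impression could feed into that.

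**Working it through.** **1. Inputs from the documents.** "Forty adult subjects will be randomized 1:1 to PH94B or placebo", so 20 per arm. The readable basis for that number is that "a clinically meaningful effect size could be estimated using a sample size of 40". No effect size, SD or dropout rate can be read (Protocol 13.2 is redacted), so there is no planned figure to reproduce. Sizes below rest on assumptions.

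**2. Imputation threshold.** 0.05 × 40 = 2. One or two missing changes give group-mean fill; three or more give multiple imputation.

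**3. Pooling early-termination scores.** With k such scores in an arm of 20, and a gap between them and the completers' mean, the arm mean moves by k × gap / 20. For k = 3 and an assumed gap of 4 to 8 points: 3 × 4 / 20 = 0.6 to 3 × 8 / 20 = 1.2 points.

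**4. Simulation, 1,000 trials per scenario.** Assumptions:
- True difference -3 points at every visit; placebo mean change -4, -7, -9, -10 at Weeks 1 to 4.
- Between- and within-subject SD of 4 each.
- Dropout unrelated to response, equally likely after Week 1, 2 or 3; the early-termination score equals the last on-treatment weekly score; 25% of leavers are lost to follow-up.
- Prohibited medication lowers later scores by 4 points.
- Multiple imputation within arm on baseline HAM-A only, 25 datasets.

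The last column keeps only scores actually taken at Week 4, with no pooling, deletion or imputation. That is the Visit 3 to 5 rule.

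| Rates, placebo / PH94B | Visit 5 | Visit 6, SAP rule | Step in size of effect | Visit 6, Visit 3-5 rule |
|---|---|---|---|---|
| No events | -3.05 | -3.06 | +0.01 | -3.06 |
| Dropout 15% / 15% | -2.91 | -2.86 | -0.05 | -2.85 |
| Dropout 20% / 5% | -2.98 | -3.40 | +0.42 | -3.00 |
| Dropout 5% / 20% | -2.97 | -2.62 | -0.35 | -3.04 |
| Prohibited medication 15% / 5% | -2.69 | -2.94 | +0.25 | -2.52 |
| Prohibited medication 15% / 15% | -3.07 | -3.04 | -0.03 | -3.03 |
| Dropout 20% / 5% and medication 15% / 5% | -2.71 | -3.44 | +0.73 | -2.55 |

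**5. Hand check of the third row.** An early-termination score falls short of the Week 4 mean by (6 + 3 + 1) / 3 = 3.33 points on average. Placebo: 20% leave and 75% of them are assessed, so 0.15 / (0.80 + 0.15) = 0.158 of the analysed scores are early, a shift of 0.158 × 3.33 = 0.53. PH94B: 0.0375 / (0.95 + 0.0375) = 0.038, a shift of 0.13. The difference moves by 0.53 - 0.13 = 0.40, against a simulated 3.40 - 3.00 = 0.40. With 15% in both arms, each arm's mean still shifts by 0.1125 / 0.9625 × 3.33 = 0.39, but the difference does not.

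**6. Imputation.** Imputed and complete-case Visit 6 estimates agree within 0.01 in every scenario.

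**7. Scale.** Under these SDs, one trial's difference has a standard error of about √(4² + 4²) × √(2/20) = 1.79. The Monte Carlo error of each tabled mean is about 1.79 / √1000 = 0.06.

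**The case against.** Several objections have force.

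- Counting early-termination scores at Visit 6 follows the stated while-on-treatment strategy. Footnote [1] discloses it, and n is shown at each visit. This stands, but nothing says that the Visit 6 figures are not comparable with the earlier ones, and the footnote does not mention the prohibited-medication deletion.
- No Week 3 versus Week 4 contrast or trend test is planned, the endpoint names Weeks 1 to 3, and the analysis is exploratory without multiplicity control. This lowers the stakes. The objective still covers all four weeks, and no Week 4 difference exists on the earlier basis.
- The complete-case analysis might seem to restore comparability. It does not: it removes imputed values but keeps the pooling and the deletion.
- A leaver is not necessarily missing from later rows, because Protocol 8.3 asks for continued weekly attendance. This stands. Those who do return would add off-treatment scores at Visits 3 to 5, where no rule is stated.
- Moving early-termination scores to the nearest week departs from SAP 6.1.5, so any such step must be a declared exception.

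A reader might also infer that the trend must shift whatever happens, or that imputation drives it. The table contradicts both: without events nothing moves, with equal rates the difference barely moves, and imputed values do not enter the descriptive series at all.

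**Conclusion.** The mismatch is real and unflagged, but its effect is conditional. A false step in the treatment difference needs discontinuation or prohibited-medication use that differs between arms. It can go either way: more placebo leavers made the effect appear to grow, and more PH94B leavers made it appear to shrink. Under the assumptions shown, it is about 0.25 to 0.7 points, which is 0.25 / 1.79 = 0.14 to 0.73 / 1.79 = 0.41 of a single trial's standard error. It is a modest bias against considerable noise.

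Larger steps can be constructed. Four leavers in one arm, none in the other, and a gap of 8 points give 4 × 8 / 20 = 1.6 points. The documents give no reason to expect that case, and it should not be read as the likely size.

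The drivers are the pooling and the Visit 6-only deletion. The by-visit descriptives use observed values but still include early-termination scores at Visit 6, and the SAP does not say whether deleted scores are also left out of them. Nothing here impugns the primary Visit 6 ANCOVA. This is a cheap improvement to an exploratory analysis.

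**What to change.** In SAP 8.3 and Table 14.2.6.1, report Weeks 1 to 4 on one basis.

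- **Preferred.** Replace the three separate ANCOVAs with one exploratory repeated-measures model: treatment, visit, treatment-by-visit, baseline and baseline-by-visit, with a stated covariance structure. Place each HAM-A at the scheduled week nearest its date, as a stated exception to SAP 6.1.5 for this analysis only, and say which score is used if two fall in the same week. Apply the same intercurrent-event rule at every visit. This model was not itself simulated.
- **Minimum.** Add a Visit 6 row to Table 14.2.6.1 under the Visit 3 to 5 rule: scores actually taken at Week 4, with no early-termination pooling and no imputation. This makes the rows comparable. It does not remove the influence of scores taken after prohibited medication, as the -2.52 in the table shows.
- **Either way.** Leave the primary ANCOVA unchanged, and footnote Table 14.2.1.1 to say that its Visit 6 row is not on the same basis as Visits 3 to 5.

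The cost is SAP wording and one model or one table row; no new data are needed. The downside is a second Week 4 estimate that may differ slightly from the primary and must be labelled exploratory.

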9.1. Adverse Events

Treatment emergent adverse events are defined as in Section 6.1.7.1. Missing and partially missing start dates will be imputed for the purpose of analysis as described in Section 6.1.8.

All AE data will be categorized as Severe > Moderate > Mild. Relationship of all AEs to IP will be categorized as related or not related. In the summaries showing severity and relationship to study drug, the event with the maximum severity or strongest relationship to study drug will be reported. If a particular event is missing the severity and/or relationship, then the strongest possible severity or relationship will be assumed for analysis (severity = severe, relationship = related).

An overall summary of TEAEs will be provided giving the number and percent of subjects who

reported at least 1 of the following: TEAE (including any TEAE, TEAEs categorized as severe, and related TEAEs), TEAE leading to discontinuation of the study drug, serious TEAEs, and TEAEs leading to death. The summary will be displayed overall and by treatment group.

In addition to the overall summary, summaries of the number and percentage of subjects with TEAEs will be displayed overall and for each treatment group by SOC and preferred term. Summaries of TEAEs by severity (Severe > Moderate > Mild) and relationship to IP (Related > Not Related) will also be provided. Treatment emergent AEs resulting in discontinuation of study drug will be summarized separately in a similar manner.

The AE summary tables will include counts of subjects. Therefore, if a subject experiences more than 1 episode of a particular AE, the subject will be counted only once for that event. If a subject has more than 1 AE that is coded to the same preferred term, the subject will be counted only once for that preferred term. Similarly, if a subject has more than 1 AE within an SOC, the subject will be counted only once in that SOC.

Subject listings of AEs will be produced. Adverse events that are treatment emergent will be flagged.

